#### 11.3.1. Adverse Events of Special Interest

Adverse events of special interest (AESI) will include: IRs, anaphylaxis, gout flares, and cardiovascular events. All adverse events of special interest will be summarized using MTX population for MTX Tolerability Period and Safety population for Run-in and Pegloticase + IMM Period, adjudicated as well as any identified by programming. IRs and anaphylaxis will be summarized in Pegloticase + IMM Period only. An independent external adjudication committee will review reported events of infusion reactions, cardiovascular events and anaphylaxis. The AESI of gout flare will not be adjudicated.

When possible, a 12-lead ECG will be performed at the time the AESI of infusion reaction, anaphylaxis and cardiovascular event is suspected

#### Infusion Reactions (IR) and Anaphylaxis

An IR will be defined as any infusion-related AE or cluster of temporally-related AEs during the Pegloticase + IMM Period, not attributable to another cause, which occur during the pegloticase infusion and for up to 2 hours post infusion. Other AEs that occur outside of the 2-hour window following the infusion may also be categorized as an IR at the Principal Investigator's discretion. Signs and symptoms of the IR and treatments administered will be documented in the medical record and in the eCRF, and will be adjudicated.

Examples of AEs not considered possible IRs include, but are not limited to: laboratory abnormalities that are unlikely to have occurred during or within 2 hour following the infusion (e.g., anemia), gout flares, most infectious diseases, or the recurrence or worsening of a known chronic medical problem identified in the subject's medical history.

The signs and symptoms associated with each event are entered on the eCRF and will be coded with the MedDRA dictionary.

#### Anaphylaxis

Any incidence of anaphylaxis should be reported as an SAE. Anaphylaxis will be defined using the National Institute of Allergy and Infectious Diseases/Food Allergy and Anaphylaxis Network (NIAID/FAAN) criteria [Sampson et al, 2006], and will be adjudicated:

1. Acute onset of an illness (minutes to several hours) with involvement of the skin, mucosal tissue, or both (e.g., generalized hives; pruritus or flushing; urticaria, and angioedema (of lips, tongue, or uvula) and  $\geq 1$  of the following:

This document is confidential.

- a. Respiratory compromise (e.g., dyspnea, wheeze-bronchospasm, stridor, reduced peak expiratory flow, hypoxemia)
  - b. Reduced blood pressure or associated symptoms of end-organ dysfunction (e.g., hypotonia [collapse], syncope, incontinence)
2. Two or more of the following that occur rapidly after exposure to a likely allergen for that subject (minutes to several hours):
  - a. Involvement of the skin-mucosal tissue (e.g., generalized hives, itch-flush, swollen lips-tongue, uvula)
  - b. Respiratory compromise (e.g., dyspnea, wheeze-bronchospasm, stridor, reduced peak expiratory flow, hypoxemia)
  - c. Reduced blood pressure or associated symptoms (e.g., hypotonia [collapse], syncope, incontinence)
  - d. Persistent gastrointestinal symptoms (e.g., crampy, abdominal pain, vomiting)
3. Reduced blood pressure after exposure to known allergen for that subject (minutes to several hours): systolic blood pressure <90 millimeters mercury (mmHg) or >30% decrease from that subject's baseline.

Summaries of IRs and anaphylaxis will group events by 3 categories:

- anaphylaxis
- infusion reactions including anaphylaxis
- infusion reactions excluding anaphylaxis

Both the investigator reported and adjudicated events and the associated signs and symptoms, will be summarized separately by SOC, PT, severity, and the time relative to the most recent pegloticase infusion for each category above. Time relative to the most recent pegloticase infusion will be categorized as: during infusion, ≤ 2 hours after infusion, > 2 hours to 24 hours after infusion, > 24 hours after infusion, and missing. Serious events and the associated symptoms will be summarized by SOC and PT. The number of events per subject, the number of events and serious events per infusion, and the number of subjects with the first event by infusion number will be summarized as well for each category. IRs (including anaphylaxis) that occur on the same date will be considered one event.

In addition, the number and percentage of subjects with adjudicated infusion reactions including anaphylaxis will be summarized overall and by severity of event by the following categories for both anti-PEG and anti-uricase antibodies:

- ADA status at baseline (positive or negative)
- ADA status post-baseline (positive or negative):
  - ADA positive during treatment is defined as
    - Negative at baseline and positive at any post-baseline timepoint, or

This document is confidential.

- Positive at baseline and had an increase in titer
- ADA negative post-baseline is defined as
  - Negative at all time points
  - Positive at baseline, but titer did not increase from baseline

Time to first infusion reaction or anaphylaxis (Kaplan-Meier analysis) will be plotted. Time to first infusion reaction or anaphylaxis for subjects who experience infusion reaction or anaphylaxis (continuous variable descriptive stats) will be summarized. Subjects who do not experience an event will be censored at the date of their last pegloticase infusion.

### Cardiovascular Events

Cardiovascular events will include Major Adverse Cardiovascular Events (MACE).

Any MACE including Non-fatal myocardial infarction, non-fatal stroke, cardiovascular death, and congestive heart failure. Following search algorithm will be used to identify possible MACE:

- For cardiovascular death (for fatal cases only):
  - Standardized MedDRA Queries (SMQ): Myocardial infarction, Ischaemic Central Nervous System (CNS) Vascular conditions (narrow); Haemorrhagic central nervous system vascular conditions (narrow), Central nervous system vascular disorders, not specified as haemorrhagic or ischaemic (narrow), Embolic and thrombotic events (arterial, venous, vessel type unspecified and mixed arterial and venous) (narrow), Cardiac failure (broad), shock-associated conditions (narrow), Torsade de pointes/QT prolongation (narrow), Arrhythmia related investigations, signs and symptoms, Cardiomyopathy, Supraventricular tachyarrhythmias (narrow), Ventricular tachyarrhythmias (narrow), Conduction defects (narrow)
  - All PTs under SOC of Cardiac disorders
  - HLGT Aneurysm
- For non-fatal myocardial infarction: SMQ Myocardial infarction
- For non-fatal stroke: SMQ: Ischaemic Central Nervous System (CNS) Vascular conditions; Haemorrhagic central nervous system vascular conditions; Central nervous system vascular disorders, not specified as haemorrhagic or ischaemic
- Congestive heart failure: SMQ Cardiac failure

Using the safety population, the cardiovascular events identified using the aforementioned criteria and the adjudicated cardiovascular events will be summarized by SOC and PT for the Run-in Period and Pegloticase + IMM Period.

### Gout Flares

The number and percentage of subjects who experienced a gout flare (recorded in the AE eCRF), and number of gout flare per subject will be summarized for the MTX Tolerability Assessment

This document is confidential.

Period using the MTX population. The number and percentage of subjects who experienced a gout flare and number of gout flares per subject during the Run-in Period and pegloticase + IMM Period (recorded in the AE eCRF) will be provided for the safety population. These events will be further summarized by month of occurrence. For the full pegloticase + IMM period, percentages will be calculated using the number of subjects in the safety population. For month 1, percentages will be based on the number of subjects in the safety population. For the other months of the pegloticase + IMM period, percentages will be based on the number of subjects who had follow-up at least through the start point of the period-specific time period. The 30 days following the end of treatment are included in the follow-up time period. For example, to be included in the Month 2 denominator, the subjects need to have received pegloticase, methotrexate, or placebo with the study day relative to the first pegloticase infusion  $\geq 31$  days. One month is defined as 30 days. Incidence of gout flares by severity will be summarized overall and by month. These events will be further summarized as occurring from the period from Day 1 to Week 12, after Week 12 – Week 24, after Week 24 – Week 36, and after Week 36 – Week 52. Events are summarized for each period according to the onset date of the flare, and only summarized in the period of onset.

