### **11.3. Adverse Events**

All adverse events will be coded using MedDRA version 23.1. AE monitoring will begin from the signature of the Informed Consent Form (ICF) until the 6 month Post Treatment Follow-up Visit. SAE monitoring will begin from the signature of the ICF until the 6 month Post Treatment Follow-up Visit.

Adverse events with an onset date strictly prior to the first MTX treatment in the MTX Tolerability Assessment Period will be called non-treatment-emergent events.

Treatment-emergent AEs (TEAEs) for the MTX Tolerability Assessment Period are defined as events with an onset date on or after the first dose of MTX (but not on or after the first MTX or placebo date in subjects who entered the Run-in Period) through 30 days after the last dose of MTX for subjects who did not receive MTX or placebo in Run-in Period.

Treatment-emergent AEs (TEAEs) for the Run-in period are defined as events with an onset date and time on or after the first dose of MTX or placebo in the Run-in Period (but not on or after the first infusion date of pegloticase in subjects who entered the Pegloticase + IMM Period) through 30 days after the last dose of MTX or placebo for subjects who did not receive pegloticase.

TEAEs for the Pegloticase + IMM Period are defined as events that occur on or after the start date and time of the first pegloticase infusion through 30 days after the last dose of pegloticase and/or MTX or placebo (whichever is later).

Adverse events with an onset date more than 30 days after the last dose of pegloticase and/or MTX or placebo (whichever is later), will be adverse events in the follow-up period.

All AEs, both serious and non-serious, will be assessed for severity using the Rheumatology Common Toxicity Criteria (CTC) v2.0. Missing data conventions for AEs are described in Section 6.3.2. The imputed onset dates will be used to determine the period of onset. Summaries of TEAEs in the MTX Tolerability Assessment Period will be provided using the MTX Population. Summaries of TEAEs in the Run-in Period and in the Pegloticase + IMM Period will be provided for the safety population.

An overall summary of TEAEs will be provided for the MTX Tolerability Assessment Period. TEAEs will be presented by treatment group for the Run-in Period and Pegloticase + IMM Period. Summaries will include the number and percentage of subjects with each AE type as well as the number of events for each of the following:

This document is confidential.

- TEAEs

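### The SAP's Month 2 denominator example for gout flares contradicts its own follow-up rule, so flares can be counted in subjects missing from the denominator

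*SAP*

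**What the plan says.** SAP 11.3.1, under Gout Flares, plans flare percentages by month, overall and by severity, in the Pegloticase + IMM Period. The paragraph sets these rules:

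- Month length: "One month is defined as 30 days".
- Month 1: "For month 1, percentages will be based on the number of subjects in the safety population".
- Later months: "percentages will be based on the number of subjects who had follow-up at least through the start point of the period-specific time period".
- Credit after treatment: "The 30 days following the end of treatment are included in the follow-up time period".
- Example: "to be included in the Month 2 denominator, the subjects need to have received pegloticase, methotrexate, or placebo with the study day relative" (Day 31 or later, counted from first infusion).
- Placement: "Events are summarized for each period according to the onset date of the flare, and only summarized in the period of onset".

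The flare window comes from elsewhere. Protocol 9.5.4.8 records every gout flare as an adverse event. SAP 11.3 defines treatment-emergent events of the Pegloticase + IMM Period as running "through 30 days after the last dose of pegloticase and/or MTX or placebo (whichever is later").

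**The concern.** The example is meant to illustrate the rule, but it applies a stricter test. The rule asks whether the subject is still being followed when the month opens, with 30 days' credit after the last dose. The example asks whether the subject is still being dosed. A programmer cannot implement both.

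If the example is programmed and flares are taken from the treatment-emergent window, subjects who stopped in the preceding 30 days can add flares to the numerator without adding themselves to the denominator. The excess depends on how many subjects stopped recently, and stopping may well differ between arms. Gout flare is a named event of special interest, and Protocol 7.1.2 describes how its course changed between Months 1-3 and Months 4-6 in the phase 3 studies. An arm-dependent artefact in the monthly display could be misread as an effect of MTX.

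**Working it through.** **The plan's own figure.** With 30-day months, Month k starts on Day 30(k-1)+1. Month 2 starts on Day 30 x 1 + 1 = 31, the day in the example.

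**Rule against example.** Let L be the day of the last study dose.

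- Rule: in the denominator if L + 30 >= 31, that is L >= 1. Every infused subject still on study qualifies.
- Example: in the denominator only if L >= 31.

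The example is one full month stricter, and the same shift carries through later months. A subject with L = 15 has counted follow-up to Day 45. A flare on Day 40 is in the Month 2 numerator; the subject is outside the example's denominator.

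**Such subjects can exist.** The stopping rule can first be met at Week 4, Day 29 (Protocol 9.5.8.2.3). MTX or placebo stops with pegloticase (Protocol 9.3.3.1.1), so oral dosing does not continue past that point.

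**Size: assumptions.** The documents give neither stopping rates nor stop times by arm, so these are stand-ins:

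- Share stopping by Week 24: planned Month 6 non-response from SAP 3.6, 1 - 0.71 = 29% on MTX and 1 - 0.43 = 57% on placebo.
- Stops fall at the 11 infusion visits from Week 4 to Week 24, in three patterns: equal shares; constant hazard per visit (1 - 0.71^(1/11) = 3.1% on MTX, 1 - 0.43^(1/11) = 7.4% on placebo); or front-loaded, with weights 1, 0.8, 0.6, 0.4, 0.3, then 0.05 six times (sum 3.4).
- Last dose: either an oral dose 2 days before the stopping visit, or the previous infusion 14 days before it.
- True flare rate: 0.5 per 30 days in both arms, before and after stopping.

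A subject followed for d days of Month 2 flares with probability 1 - exp(-0.5d/30). For the full month this is 1 - exp(-0.5) = 39.3%. For L below 31, d = min(30, L).

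*Smallest case (equal shares, oral dose).* Only Week 4 stoppers are excluded: L = 29 - 2 = 27, d = 27, probability 1 - exp(-0.45) = 0.362. Their share is 0.29/11 = 0.026 on MTX and 0.57/11 = 0.052 on placebo.

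- MTX: (0.974 x 0.393 + 0.026 x 0.362)/0.974 = 40.3%.
- Placebo: (0.948 x 0.393 + 0.052 x 0.362)/0.948 = 41.3%.

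*Largest case (front-loaded, last infusion).* Week 4 stoppers have L = 15 (probability 0.221) and Week 6 stoppers L = 29 (0.383). Their shares are 0.29 x 1/3.4 = 0.085 and 0.29 x 0.8/3.4 = 0.068 on MTX, and 0.168 and 0.134 on placebo.

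- MTX: (0.846 x 0.393 + 0.085 x 0.221 + 0.068 x 0.383)/0.846 = 44.7%.
- Placebo: (0.698 x 0.393 + 0.168 x 0.221 + 0.134 x 0.383)/0.698 = 52.0%.

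All six Month 2 cases, with the same numerator over each denominator (gaps from unrounded values):

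| Stop pattern | Last dose | Example: MTX v placebo | Gap (points) | Rule: MTX v placebo |
|---|---|---|---|---|
| Equal shares | oral | 40.3% v 41.3% | 1.0 | 39.3% v 39.2% |
| Equal shares | infusion | 41.0% v 42.8% | 1.8 | 38.9% v 38.4% |
| Constant hazard | oral | 40.5% v 42.2% | 1.7 | 39.3% v 39.1% |
| Constant hazard | infusion | 41.3% v 44.3% | 3.0 | 38.8% v 38.0% |
| Front-loaded | oral | 42.7% v 46.6% | 3.9 | 39.1% v 38.8% |
| Front-loaded | infusion | 44.7% v 52.0% | 7.4 | 37.8% v 36.3% |

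**What recovers the truth.** Anyone dosed on Day 31 or later is followed, with the 30-day credit, through all of Month 2. Keeping the example's denominator and counting flares only in those subjects returns 39.3% in both arms. The rule's denominator alone does not: it includes subjects followed for part of the month and reads slightly low, more so on placebo here. Flares per 30 person-days return 0.50 in both arms.

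**Direction in later months.** With placebo stopping front-loaded and MTX stopping at constant hazard (last infusion), the ratio of rule to example denominator in Months 5-6 is 1.06 on MTX and 1.04 on placebo. The order has reversed.

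**The case against.** Four arguments have force.

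**The numerator mismatch is inferred.** The Gout Flares paragraph does not cite the treatment-emergent window, and its onset-date sentence follows the 12-week blocks. The table index is redacted, and SAP 13.2.5.2 asks for careful choice of denominators, documented in footnotes or programming notes. A programmer might match the two sets without being told. This stands as a caution about what will be programmed. It does not remove the contradiction: that sentence is worded for every period, and nothing restricts flares to subjects in the denominator.

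**The size depends on stop timing.** If the last weekly oral dose counts, as the example allows, Week 6 stoppers usually stay in and the gap can be as small as 1 point. This stands, and is why a range is given.

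**Non-response is not stopping.** A reader might take 29% and 57% as the plan's stopping rates. They are not: under SAP 9.2.2, missing data also make a non-responder, as does less than 80% of time below threshold without stopping.

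**The example's denominator is not the worse one in itself.** With a matched numerator it gives the correct figure in this model, while the rule's denominator is slightly low. So the remedy is not simply to swap denominators.

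One defence fails: that the 30 days belong to the separate follow-up period. SAP 11.3 starts that period more than 30 days after the later last dose.

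**Conclusion.** The contradiction is plain on the page and should be resolved before programming. Followed as written, the example overstates monthly flare percentages, generally more in the arm with more stopping in the preceding 30 days. Under the proxy stopping rates and an equal assumed flare rate, the spurious Month 2 gap is about 1 to 7 points, placebo higher.

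A reader might infer that the plan will produce a false flare benefit for MTX. The documents do not support that as a general claim: stopping by arm is unknown, the numerator set is not stated outright, and the order can reverse in later months.

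Nor is any formal comparison at risk. The full-period percentage uses the safety population, and neither it nor the Fisher test on special-interest events (Protocol 9.6.7) uses this denominator. The effect is confined to descriptive by-month flare summaries, overall and by severity. SAP 11.3 already plans incidence per person-year for adverse event tables, but not by month.

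**What to change.** Reconcile the example with the rule in SAP 11.3.1, and state that numerator and denominator use the same subjects. Either option works:

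- **(a)** Keep the Day 31 dosing requirement, count flares only in those subjects, and state that flares in subjects already stopped are shown elsewhere. The monthly percentage then describes subjects still on treatment.
- **(b)** Change the example to last study dose + 30 days >= Day 31, and make flares per 30 person-days by arm the comparative monthly figure. The percentage on this denominator includes part-month follow-up and is slightly too low in the arm that stops more, so it should not carry the comparison.

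Option (b) discards no flares and keeps the stated 30-day credit. The cost is one or two sentences in the SAP and one added table row; no new data are needed.

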#### 11.4. Laboratory Evaluations

Blood (for hematology and clinical chemistry) will be collected at the Screening, Week -6 (prior to the first dose of MTX), and Week -4 and -2 Visits during the Run-in Period; prior to pegloticase infusion on Day 1 and at the Weeks 2, 6, 14, 22, 24, 36 and the non-infusion End of Pegloticase Infusions Visit (if applicable), Week 52/End of Study/Early Termination and 3 and 6 month Post Treatment Follow-up Visits.

Blood and urine samples (for allantoin) will be collected prior to the pegloticase infusion and after the end of each pegloticase infusion prior to discharge from the site on Day 1 and at Weeks 14 and 36; Additional blood and urine samples for allantoin will be collected at the End of Pegloticase Infusions Visit (if applicable) and the Week 52/End of study/Early Termination Visit.

Urine (for albumin:creatinine ratio) samples will be collected prior to the pegloticase infusion on Day 1 and at the Weeks 14, 24, 36 and the non-infusion End of Pegloticase Infusions Visit (if applicable) and Week 52/End of Study/Early Termination Visits.

Urine (for human chorionic gonadotropin) samples will be collected at all visits except the Screening Visit and Weeks 21, 23 and 3 and 6 month Post Treatment Follow-up Visits for all female subjects of childbearing potential.

Safety laboratory assessments will include:

- Hematology: complete blood count with differential (hemoglobin concentration, hematocrit, erythrocyte count, platelet count, leukocyte count, and differential leukocyte count)
- Chemistry: albumin, transaminases (aspartate aminotransferase, alanine aminotransferase), alkaline phosphatase, total bilirubin, creatinine (including calculation for Estimated Glomerular Filtration Rate (eGFR) calculated by the Modification of Diet in Renal Disease (MDRD) study equation :  $175 \times (S_{cr[mg/dL]})^{-1.154} \times (age)^{-0.203} \times (0.742 \text{ if female}) \times (1.212 \text{ if African American})$  or  $175 \times (S_{cr[\mu mol/L]})^{-1.154} \times (age)^{-0.203} \times (0.742 \text{ if female}) \times (88.4)$ )

This document is confidential.

(1.212 if African American), glucose, sodium, potassium, calcium, chloride, total protein, blood urea nitrogen, and human chorionic gonadotropin (at the Screening Visit for all female subjects of childbearing potential)

- Urine: albumin:creatinine ratio, and human chorionic gonadotropin for all female subjects of childbearing potential

Safety laboratory samples will be analyzed by the central laboratory. Samples will be collected for analysis at the local laboratory, if needed.

Laboratory results will be displayed using the conventional units for all summaries and listings. Clinical laboratory test results (hematology, chemistry, and urinalysis) and their changes from baseline will be summarized by pegloticase treatment status (On Treatment, Post-Treatment, and Overall, see Section 9.4), visit, and treatment group for the safety using descriptive statistics.

If a continuous laboratory value is reported as either below or above the limits of quantification, the qualifiers will be dropped and the numeric value used in the analysis (e.g., “< 3” will be summarized as “3” and “> 200” will be summarized as “200”).

For all laboratory tests, results will be categorized as low, normal, or high based on their normal ranges. Results out of range will be identified as such on subject listings.

Using the safety population , shift tables using categories of low, normal, and high, comparing laboratory test results from baseline to each visit will be presented with percentages based on subjects with a non-missing value at baseline and post-baseline visit. A summary of elevated liver function test values as well as Hy’s law will be provided by visit and for any post-baseline visit:

- alanine aminotransferase > ULN, 2xULN, 3xULN, 5xULN, 10xULN, and 20xULN
- aspartate aminotransferase > ULN, 2xULN, 3xULN, 5xULN, 10xULN, and 20xULN
- alkaline phosphatase  $\geq$  1.5xULN, 2.5xULN, and 3xULN
- total bilirubin  $\geq$  1.5xULN, 2xULN, and 3xULN

Hy’s law:

- (alanine aminotransferase or aspartate aminotransferase  $\geq$  3xULN) and total bilirubin  $\geq$  2xULN
- (alanine aminotransferase or aspartate aminotransferase  $\geq$  3xULN) and total bilirubin  $\geq$  2xULN and alkaline phosphatase < 2xULN

For tests where the Common Terminology Criteria for Adverse Events (CTCAE) criteria is available, shift tables will be based on the CTCAE grade. The CTCAE version 4.03 will be used for these summaries. Laboratory results as well as results out of normal range will be presented in listings.

